Data analysis	Sample attrition at each step of the inclusion-exclusion criteria will be provided. We will develop the breakdown of the distribution of demographic, comorbidity, and baseline measures prior to and after the PSM (unmatched and matched cohorts). Significance of differences will be tested at $P<0.05$ for the matched cohort. Additionally, we will consider the use of standardized mean differences as noted above, in which $SMD <0.1$ indicates balance. The primary endpoint measure is time to first severe exacerbation and severe exacerbation will be defined as a hospitalization or an ER visit with a primary diagnosis of asthma. We will calculate the time in days to first exacerbation. We will conduct Cox proportional hazards modeling to estimate the risk of exacerbation and provide corresponding KM curves for the primary endpoint. Exposure to each of the study comparators (ICS+Tio and ICS/LABA) will be recorded using time-varying covariates for all primary and secondary endpoints. ICS+Tio vs. ICS/LABA will be the key independent variable and medication exposure will be a covariate included in the regression. Secondary endpoints will include time (in days) to first moderate-or-severe exacerbation defined as use of systemic corticosteroid or a hospitalization or ER visit with a primary diagnosis of asthma. Cox PH and KM curves will be conducted for this secondary end point as well. We will also calculate and compare the rate of exacerbation, proportion of patients with exacerbations after 6 months and one year among the sub-population of patients having at least 6 months and a one year of follow-up, respectively. We will report rates in patient-years to account for variable follow-up time. We will also compare the mean monthly (to account for variable follow-up time) per patient HCRU (all-cause and asthma related hospitalizations, ER visits, and outpatient visits) during the follow-up period, between the two groups. Proportions of patients with and without rescue medication use will be compared between the two groups as well.
----------------------	--

Proprietary confidential information © 2021 Boehringer Ingelheim International GmbH or one or more of its affiliated companies

5 . AMENDMENTS AND UPDATES

None

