6. MILESTONES

Study design and core group alignment	Week 1-2
Data receipt, extraction, cleaning and evaluation for protocol development	Week 2
Study protocol draft	Week 4
Study protocol final	Week 6
IET/NPCC approval	Week 8/9
Descriptive statistics draft	Week 11-12
Multivariate analysis draft	Week 12-14
Final results (Excel)	Week 16-17
Study narrative report	Week 17-18

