Pneumonia	Identified using appropriate ICD codes. Coded as binary (yes/no) variables	PSM
Acute bronchitis	Identified using appropriate ICD codes. Coded as binary (yes/no) variables	PSM
Dyspnea	Identified using appropriate ICD codes. Coded as binary (yes/no) variables	PSM
Alcohol dependence	Identified using appropriate ICD codes. Coded as binary (yes/no) variables	PSM
Smoking dependence	Identified using appropriate ICD codes. Coded as binary (yes/no) variables	PSM

Using propensity score matching (PSM) technique, we will develop matched cohorts of patients between the ICS+Tio and ICS/LABA groups. We will conduct 1:2 matching using nearest neighbor matching approach. Upon completion of matching, we will assess whether the cohorts are balanced by examining the statistically significant differences at $p < 0.05$. We will also assess balance by calculating standardized mean differences (SMD). An SMD < 0.1 will be considered balanced. Follow-up time will be calculated between index date and 'Censor date' which will be defined as the date of either one of the following events: 1. Date of first exacerbation, 2. Date of medication switch, 3. Discontinuation of medication (defined as date of prescription claim plus days' supply, plus 50% additional days), 4. Enrollment end date, or 5. Last date available in the dataset/End of study period. In this "new user", study design, primary analysis will be an "as-treated" analysis. In order to attribute events and outcomes to patients during the time that they are exposed to treatment (based on days-supply of prescription claims + a buffer window) as well as account for differences in inter-group adherence levels, we will use a time-varying covariate approach to classify drug exposure time for each comparator drug during follow up. This approach has been chosen to minimize bias based on potentially large differences in medication adherence rates, by only attributing outcomes to the time in which patients have medication in their possession based on days' supply as described below. For each individual study drug, we will identify and define medication exposure and non-exposure windows during the follow-up time for each medication using the date of prescription filled plus the days' supply listed on the prescription claim plus 50% additional days (to account for residual doses in canister, poor real-world adherence and latency of drug effects). For example, exposure start and stop dates

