Proprietary confidential information © 2021 Boehringer Ingelheim International GmbH or one or more of its affiliated companies for a patient with a prescription claim with 30 days supply on January 1st will be January 1st and February 15th respectively (30 days' supply +15 days). We will run sensitivity analyses on the exposure window using 0% and 100% additional days. These time varying exposure covariates will be included in the Cox PH regression.

If statistical differences are found after PSM, then the study team will make a determination to either include them as covariates in the regression analysis (Cox PH), or develop interaction terms to match on, or discontinue the study. In the event of study discontinuation, partial results (all analysis leading up to and including PSM) will be provided in a final report.

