9.7 DATA ANALYSIS

9.7.1 Main analysis

Sample attrition at each step of the inclusion-exclusion criteria will be provided. We will develop the breakdown of the distribution of demographic, comorbidity, and baseline measures prior to and after the PSM (unmatched and matched cohorts). Significance of differences will be tested at $P<0.05$ for the matched cohort. Additionally, we will consider the use of standardized mean differences as noted above, in which $SMD <0.1$ indicates balance of baseline covariates. The primary endpoint measure is time to first severe exacerbation and severe exacerbation will be defined as a hospitalization or an ER visit with a primary diagnosis of asthma. We will calculate the time in days to first exacerbation. Also, as part of the primary end point analysis, we will develop KM curves based on initial exposure and conduct time varying Cox proportional hazards modeling accounting for changes in exposure status over the follow up time to estimate the risk of exacerbation between ICS+Tio vs. ICS/LABA. Secondary endpoints will include a number of measures. We will calculate the time in days to first moderate-or-severe exacerbation defined as use of systemic corticosteroid or a hospitalization or ER visit with a primary diagnosis of asthma. KM curves based on initial exposure and time varying Cox PH models will be conducted for this secondary end point as well. We will also calculate and compare the rate of exacerbation, proportion of patients with exacerbations after 6 months and one year among the sub-population of patients having at least 6 months and a year of follow-up, respectively. We will report rates in patient-years to account for variable follow-up time. We will also compare the mean monthly (to account for variable follow-up time) per patient HCRU (all-cause and asthma related hospitalizations, ER visits, and outpatient visits) during the follow-up period, between the two groups. Proportions of patients with and without rescue medication use will be compared between the two groups as well.

Proprietary confidential information © 2021 Boehringer Ingelheim International GmbH or one or more of its affiliated companies

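### The action rule after matching is triggered by undefined statistical differences, most naturally p < 0.05, so it depends on sample size and can depart from the protocol's own SMD < 0.1 definition of balance

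*Combined protocol and SAP*

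**What the plan says.** Section 9.1 gives two balance checks for the matched cohorts. The first is a test: "we will assess whether the cohorts are balanced by examining the statistically significant differences at" p < 0.05. The second is an effect-size rule: "An SMD < 0.1 will be considered balanced". No section says which prevails when they disagree.

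The Abstract (data analysis) and section 9.7.1 pair the same two measures. Section 9.7.1 has "Significance of differences will be tested at" P < 0.05 in the matched cohort, and both places then say "Additionally, we will consider the use of standardized mean differences as noted above". In these two places the word balance is attached only to the SMD. Section 9.1 alone ties the p-value to balance expressly.

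The action rule closes section 9.1: "If statistical differences are found after PSM, then the study team will make a determination to either include them as covariates" in the Cox regression, "or develop interaction terms to match on, or discontinue the study". It states no threshold, and it gives no criterion for choosing among the three responses. If the study is discontinued, "partial results (all analysis leading up to and including PSM) will be provided in a final report".

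On timing, section 6 places the descriptive statistics draft in weeks 11-12 and the "Multivariate analysis draft" in weeks 12-14. Section 9.2.4 lists the sponsor's grounds for discontinuing the study; residual imbalance is not one of them.

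**The concern.** The size of an imbalance and its p-value are different things. The SMD measures how far apart the groups are on a covariate. The p-value also reflects how many patients were matched. A p-based trigger can therefore fire or stay silent on the same residual imbalance according to sample size alone.

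The three responses differ greatly in weight. One changes the model for the primary endpoint, one changes the matched cohort, and one ends the comparison. If the trigger is the p-value, any of them could follow from a covariate that section 9.1 calls balanced. In a small matched sample, a covariate that fails the SMD rule could pass without action. In both cases the next step is left to the study team, with no order stated in advance.

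**Working it through.** The plan gives no figure on this point to reproduce. The check is whether the two criteria can disagree, and at what sample sizes.

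**Inputs from the documents**
- Significance level 0.05, and SMD limit 0.1 (section 9.1).
- Matching 1:2 (section 9.1), taken as one ICS+Tio patient to two ICS/LABA patients.
- 17,882 tiotropium patients after the COPD exclusion (section 9.5). This is a ceiling, because further criteria and the concurrent-ICS restriction are still to be applied.

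**Assumptions**
- A two-sided test of independent groups, normal approximation, with every ICS+Tio patient receiving two comparators. The plan does not name the test.
- All values of n other than 17,882, because the matched size is not stated.

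**Formula.** With n matched ICS+Tio patients and 2n comparators, p < 0.05 when

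|SMD| > 1.96 × √(1/n + 1/(2n)) = 1.96 × √(1.5/n).

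**Where the criteria coincide.** Setting the right side to 0.1 gives n = 1.5 × (1.96/0.1)² = 1.5 × 384.16 ≈ 576.

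**Smallest absolute SMD that reaches p < 0.05**

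| Matched ICS+Tio patients | Threshold |
|---|---|
| 300 (assumed) | 0.139 |
| 576 (crossover) | 0.100 |
| 1,000 (assumed) | 0.076 |
| 5,000 (assumed) | 0.034 |
| 17,882 (ceiling) | 0.018 |

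For example, at 1,000: 1.96 × √0.0015 = 1.96 × 0.0387 = 0.076.

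**Above the crossover.** Take an SMD of 0.05, which section 9.1 calls balanced. At n = 1,000, z = 0.05/0.0387 = 1.29 and p = 0.20. At n = 5,000, z = 0.05/0.0173 = 2.89 and p = 0.004. It reaches p = 0.05 at n = 1.5 × (1.96/0.05)² ≈ 2,305. The imbalance is the same throughout; only the sample size changes.

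**Below the crossover.** At n = 300, an SMD of 0.12 gives z = 0.12/0.0707 = 1.70 and p = 0.09. It fails the SMD rule but would not fire a p-based trigger.

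**Sensitivity of the crossover.** With one comparator per ICS+Tio patient it is 2 × 384.16 ≈ 768. If the test allows for a within-set correlation ρ, it is 1.5 × (1 − ρ) × 384.16, or about 520 at ρ = 0.1 and about 400 at ρ = 0.3. These assumptions move the crossover but do not remove it.

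**The case against.** The strongest reply is that the conflict depends on a reading. The action rule says *statistical differences*, where the balance sentence says statistically significant differences, and it follows an assessment that uses both measures. It can fairly be read as asking the team to look at both and then judge. A reader might infer that the protocol flatly contradicts its own definition of balance. The text does not support that much: on the broader reading the rule is unspecific, not contradictory. What stands is that the broader reading still leaves no way to settle a disagreement between the two measures, and that the p < 0.05 reading is the more natural one because it has the nearest matching wording.

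A reader might also infer that the team could choose its response after seeing outcomes. The documents do not show this. Limiting the partial report to work up to matching suggests that balance is judged first, and a decision to re-match or stop taken before outcomes are seen does not select on results. But no sentence says so, and the milestones are weak support because the two drafts overlap at week 12.

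A third reply is that adding a covariate with a small SMD to the Cox model would usually change little. That is fair for the first response. It does not cover re-matching or discontinuation.

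Finally, removing p < 0.05 from the balance assessment goes further than consistency strictly requires, since a sponsor could pre-specify a combined rule. That is true. But any rule that acts on the p-value keeps the dependence on sample size, whereas the SMD limit is already in the protocol.

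**Conclusion.** The point holds in a limited form and should be corrected. The trigger is undefined and most naturally means p < 0.05. On that reading it agrees with the protocol's SMD limit only near 576 matched ICS+Tio patients. Above that size it can act on covariates the protocol calls balanced; below it, it can miss an SMD of 0.1 or more.

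This rests on the natural reading of the trigger, on full 1:2 matching, and on a two-sided independent-groups test. Apart from the 17,882 ceiling, every sample size used is illustrative.

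It would be tempting to conclude that the study will be stopped or re-matched needlessly, or that the primary hazard ratio is biased. Neither follows. The matched size and the residual imbalances are unknown, so the frequency of a conflict cannot be predicted, and nothing in the documents gives its effect on the hazard ratio. The missing precedence between criteria and the unordered responses are gaps in specification. The substantive improvement is to replace a trigger that depends on sample size with the threshold the protocol has already adopted.

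**What to change.** **Main change.** In the action rule of section 9.1, replace the undefined term with |SMD| ≥ 0.1. Make the same threshold the governing balance criterion in the Abstract, in the balance paragraph of section 9.1 and in section 9.7.1. P-values may stay as description, but not as a trigger for action or discontinuation.

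**Secondary wording**
- State that the decision is made before outcomes are examined.
- Pre-state the order of responses. One example is to refine the propensity model with interaction terms and re-match, then add any covariate still at |SMD| ≥ 0.1 to the Cox model. The order is the sponsor's choice.
- If discontinuation for imbalance is kept, give an SMD-based condition for it and align section 9.2.4.

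**Cost.** Protocol wording only. The SMDs are already planned, so no new data or analysis is needed.

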9.3.3 Covariates

The covariates included in the PSM will be

- Gender
- Age group
- Region
- ICS dose level
- Control level
- Rescue medication use
- Comorbidities included in the Charlson Comorbidity Index
- ICS history (yes/no)
- ICS history duration
- Season of index date
- Index year
- Baseline all-cause resource use (presence vs. absences of hospitalizations, or ER visits, or outpatient visits)
- Baseline other asthma medications (use vs. no use)

Proprietary confidential information © 2021 Boehringer Ingelheim International GmbH or one or more of its affiliated companies

- Baseline overall medication history (polypharmacy defined as number of unique medications)
- Insurance type
- Hypertension
- Gastroesophageal reflux disease
- Allergic Rhinitis
- Obesity
- Sinusitis
- Obstructive sleep apnea
- Cardiovascular disease
- Diabetes
- Renal failure
- Arthritis
- Osteoporosis
- Depression
- Cancer (excluding basal cell carcinoma)
- Baseline pneumonia diagnosis
- Baseline acute bronchitis diagnosis
- Diagnosis of dyspnea during baseline identified using ICD 9 786.0x and ICD 10 R06.0x
- Diagnosis of alcohol dependence during baseline identified using ICD 9 303.xx, 305.0x and ICD 10 F10.xx
- Smoking dependence during baseline identified using ICD 9 305.1 and ICD 10 F17.xx

In addition to the key independent variable of interest (ICS+TIO vs ICS/LABA group), we will include time varying medication exposure as a covariate in the regression.

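### If imbalance left after matching is handled by covariate adjustment, the plan adjusts only the Cox models and leaves the rate, proportion, HCRU and rescue-use comparisons unadjusted

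*Combined protocol and SAP*

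**What the plan says.** Section 9.1 plans 1:2 nearest-neighbor matching. It judges balance in two ways: by significance tests at p<0.05, and by SMD, where "An SMD < 0.1 will be considered balanced". It then sets out what follows a failed check. The choice rests with the team, which may "include them as covariates in the regression analysis (Cox PH), or develop interaction terms to match on, or discontinue the study". There is no order of preference and no rule for choosing. If the study is discontinued, "partial results (all analysis leading up to and including PSM) will be provided in a final report".

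Section 9.7.1 names a time-varying Cox model for time to first severe exacerbation and for time to first moderate-or-severe exacerbation. For the other secondary endpoints it names a comparison but no model and no covariates:

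- Exacerbation rate and proportion: "We will also calculate and compare the rate of exacerbation, proportion of patients with exacerbations after 6 months and one year".
- Rescue medication: "Proportions of patients with and without rescue medication use will be compared between the two groups as well".
- HCRU: mean monthly use per patient is compared between the groups.

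Section 9.3.3 lists "Rescue medication use" among the matching covariates. Its follow-up counterpart is the section 9.3.2.2 endpoint, the proportion of patients with one or more SABA claims.

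**The concern.** The covariate option keeps a cohort in which a difference has been detected and relies on the outcome model to remove its effect. That works only where there is an outcome model. For the exacerbation rate, the 6-month and one-year proportions, HCRU and rescue use, matching is the only protection against baseline differences that the plan describes. On this branch, matching is known to have left some.

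One report could then show hazard ratios adjusted for, say, baseline rescue use beside a raw comparison of follow-up rescue use from the same patients. A reader could not tell whether a difference in the second came from treatment or from the imbalance already found. The primary endpoint and the time-to-event secondary endpoint are not affected.

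**Working it through.** The plan gives no final sample size, power or effect size, so there is no stated figure to reproduce. The check has a textual part and an illustration.

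**1. Reach of each permitted action**

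| Action in 9.1 | Two Cox endpoints | Rate, proportions, HCRU, rescue use |
|---|---|---|
| Covariates in the Cox model | Adjusted | No adjustment specified |
| Interaction terms to match on | New matched cohort | New matched cohort |
| Discontinue | Not reported | Not reported |

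Only the first row treats the endpoints differently. Three other statements might seem to fill the gap:

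- The abstract says exposure is recorded with time-varying covariates for all endpoints, but this concerns drug exposure.
- The regression covariate in 9.3.3 is also medication exposure.
- Rates in patient-years and monthly HCRU deal with length of follow-up.

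None of these adjusts for a baseline difference.

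**2. How easily the branch is reached**

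With n ICS+Tio and 2n ICS/LABA patients, the standard error of a standardized difference is SE = sqrt(1/n + 1/(2n)) = sqrt(1.5/n). The smallest SMD reaching two-sided p<0.05 is 1.96 × SE. Sizes other than 17,882 are assumed; 17,882 is the section 9.5 count after the COPD exclusion and before further criteria.

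| n | SE | Smallest SMD at p<0.05 |
|---|---|---|
| 1,000 | 0.0387 | 0.076 |
| 3,000 | 0.0224 | 0.044 |
| 8,000 | 0.0137 | 0.027 |
| 17,882 | 0.0092 | 0.018 |

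All lie below 0.1, so the p-value criterion can flag a variable that the SMD criterion passes. Section 9.3.3 lists 33 matching covariates. If the tests were independent and each had its nominal 5% rate, the chance of at least one flag would be 1 − 0.95^33 = 0.82. This is a rough guide: the tests are not independent, and matching can balance covariates more closely than chance would.

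**3. What an unadjusted comparison carries**

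Take no true treatment effect, and one unbalanced variable with correlation ρ to the outcome (assumed). Then bias = SMD × ρ in SD units, and the false-positive rate is P(|Z + bias/SE| > 1.96).

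*Imbalance just reaching p<0.05.* Here SMD = 1.96 × SE, so bias/SE = 1.96ρ whatever n is:

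- ρ = 0.3: bias/SE = 0.588, false-positive rate 9.0%.
- ρ = 0.5: bias/SE = 0.98, false-positive rate 16.5%.

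*SMD 0.10*, the limit of the plan's own SMD criterion (bias 0.03 SD at ρ = 0.3, 0.05 SD at ρ = 0.5):

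| n | bias/SE, ρ = 0.3 | False-positive rate | bias/SE, ρ = 0.5 | False-positive rate |
|---|---|---|---|---|
| 1,000 | 0.77 | 12% | 1.29 | 25% |
| 3,000 | 1.34 | 27% | 2.24 | 61% |
| 8,000 | 2.19 | 59% | 3.65 | 95% |

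*SMD 0.05:* 7%, 10% and 19% at ρ = 0.3, and 10%, 20% and 45% at ρ = 0.5. With n = 1,000 this SMD would not reach p<0.05.

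The formula treats the SMD as a systematic difference with full sampling variation around it. Conditioning on the observed imbalance replaces Z by sqrt(1 − ρ²) × Z. The just-significant case then gives 8% (ρ = 0.3) and 13% (ρ = 0.5), and SMD 0.10 with ρ = 0.5 gives 22%, 63% and 97%. The message is the same.

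**4. The same bias as a ratio**

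For one binary confounder with prevalence p1 and p0 in the two groups and outcome risk ratio RR, the crude ratio under no effect is (1 + p1(RR − 1)) / (1 + p0(RR − 1)). With p0 = 0.20, SMD 0.10 gives p1 = 0.2414. RR = 2 then gives 1.2414/1.20 = 1.03, and RR = 3 gives 1.4828/1.40 = 1.06. Across assumed prevalences of 20% to 50% and RR of 2 to 3, the crude ratio is about 1.02 to 1.03 at SMD 0.05, 1.03 to 1.06 at 0.10 and 1.07 to 1.12 at 0.20.

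**The case against.** A reader might infer that Cox covariates are the only remedy, so that these comparisons are bound to carry any known imbalance. The documents do not support that. Re-matching on interaction terms changes the cohort for every endpoint, and discontinuation leaves no outcome result to bias. The problem arises on one branch of three.

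A reader might also infer that baseline values such as rescue use go unused. They are used: rescue use, control level and all-cause resource use are all matching covariates, and Table 1 gives matching as the adjustment method for every variable it lists. A comparison in a well-matched cohort is adjusted by design, and adding the same baseline value to the outcome model would then mainly gain precision. This stands, but it does not answer the case where matching has left a difference.

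The abstract's wording on time-varying covariates for all endpoints, followed by a reference to the regression, could suggest modelling beyond the Cox endpoints. It names no model type and no baseline covariates, so it does not close the gap.

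On size, it would be selective to argue that the branch is likely because tiny SMDs reach p<0.05 and then quote the harm only at SMD 0.10, which already fails the plan's SMD criterion. An imbalance that only just reaches p<0.05 does much less damage, and for a single confounder with SMD at or below 0.1 the shift in a ratio is modest.

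**Conclusion.** The point holds conditionally. If the team chooses covariate adjustment for imbalance left after matching, the plan corrects the two Cox analyses and specifies no corresponding adjustment for the exacerbation rate, the exacerbation proportions, HCRU or rescue use.

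The consequence ranges from slight (a false-positive rate of about 9% to 17% for a just-significant imbalance) to serious (25% to 95% at SMD 0.10 and correlation 0.5, depending on sample size). These figures rest on assumed sample sizes and correlations, on the 1:2 ratio, and on a single unbalanced variable that predicts the endpoint concerned. Only secondary results are at risk. The gap should be closed before analysis, because the repair is cheap and the p-value criterion makes this branch a realistic one.

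**What to change.** **Section 9.1.** In the sentence on differences remaining after matching, replace the reference to the Cox regression with: *in the outcome models for all endpoints, Cox and non-Cox*.

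**Section 9.7.1, and the abstract to match.** Analyse the non-Cox secondary endpoints with regression models. Each contains treatment group, the baseline counterpart of the measure where collected (for example baseline rescue use for follow-up rescue use), and any variable still unbalanced after matching:

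- Exacerbation rate: Poisson with robust variance and a log person-time offset. Section 9.1 ends follow-up at the first exacerbation, so each patient contributes at most one event; use negative binomial only if later events are counted.
- HCRU: count models with a log person-time offset.
- Proportions with exacerbation at 6 months and one year: logistic or robust Poisson.
- Rescue use: a model that accounts for follow-up time, because the endpoint is any SABA claim during a follow-up of variable length.

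Keep the unadjusted comparisons as descriptive.

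**Cost.** Protocol wording and a few more models, with no new data. The small downside is that these secondary results become model-based.
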